1. a. Medication Discrepancies, Adverse Drug Events and Hospital Utilization.

Medication discrepancies are defined as unintentional differences found in the patient's medical record compared with the patient's medication information.⁷ Discrepancies may be commissions, omissions, duplications or alterations in dose or frequency. Medication discrepancies are associated with adverse drug events (ADEs), which are broadly defined as "injury resulting from the use of a drug."⁸ In the US, ADEs result in 7,000 deaths annually and cost the health system \$4.2 billion. One in four ambulatory patients in experience

ADEs,^{9,10} while as many as 60% of patient records contain medication discrepancies.¹¹⁻¹³ Patients experiencing transitions in care, such as hospital discharge, are particularly vulnerable to medication discrepancies and ADEs, the latter occurring in as many as one in five patients within 30 days of discharge.¹⁴⁻¹⁶ Medication discrepancies and ADEs are a major contributor to hospital utilization among patients recently discharged from the hospital,¹⁷ a period frequently marked by multiple medication changes, alterations in health status, and extended period of time before return to primary care. Among patients discharged from the hospital, 14-20% will be readmitted within 30 days,^{18,19} and more than 30% will seek emergency care during the same period.²⁰ *While numerous tools and approaches have been developed to improve care transitions,²¹ medication safety after discharge remains a concern.²²*

2. b. Medication Reconciliation: Policies and Approaches.

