discharge. Because the attachment feature of SM was not available at the time of the pilot, we instead used a text-based format, embedded in the body of the SM (figure 1 in Appendix 2), for the pharmacist and Veteran to reconcile medications. As we will do in the proposed SMMRT Trial, we recruited hospitalized Veterans, registered them for MHV, and trained them to use MHV and SMMRT. After discharge, our pharmacist reviewed the CPRS records of 51 eligible Veterans and identified 108 clinically important medication discrepancies (median 2 per Veteran), mostly medications that the Veteran was taking but were omitted from the

discharge summary or discharge medication list. After correcting these discrepancies, the pharmacist sent SMMRT via SM to the Veteran. A total of 34 Veterans (67%) returned SMMRT. Of these 34 Veterans, 17 (50%) had additional discrepancies, most commonly duplicative medications prescribed for the Veteran at VA Boston and another VA facility. Nine of 10 Veterans completing post-intervention in-depth interviews (similar to those proposed in Aim 3) said they would use SMMRT again. Appendix 5 presents direct quotes about SMMRT from these Veteran participants. This study demonstrated the feasibility of recruiting hospitalized Veterans and training them in MHV and SM. Results highlighted the high prevalence of medication discrepancies immediately after discharge and the ability to detect and correct them by SMMRT.

#Aligning Medication Reconciliation and SM: A Qualitative Study of Providers' Perspectives.

In this study, published in *JMIR*,³⁹ we conducted in-depth interviews with 15 primary care providers to characterize ambulatory medication reconciliation, the use of SM in primary care, and perceptions of a SMMRT-like medication reconciliation system. Providers recognized the value of medication reconciliation, especially after hospital discharge, and suggested numerous challenges to medication reconciliation. Providers emphasized the importance of collaborating with pharmacists in reviewing Veterans' medication regimens.

#Qualitative Study of Pharmacists' Role in Medication Review and Reconciliation.

[name] recently completed a series of interviews with clinical pharmacists regarding their role in medication management. Preliminary analyses revealed considerable enthusiasm among pharmacists for developing relationships and monitoring patients to improve medication safety.

#Medication Discrepancies.

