We evaluated the accuracy of VA's computer-generated medication listing to determine prevalence of

medication discrepancies; 60% of ambulatory Veterans had at least one medication discrepancy.¹³
#Usability Studies.

Colleagues Drs. [name] and [name] have conducted research at the VA HSR&D Human-Computer Interaction Laboratory in Indianapolis, IN that directly informs this investigation. These studies have included usability testing with VA patients or providers. For example, in a study published in *JAMIA*, [name] and colleagues evaluated usability of basic MHV features.⁴¹ In this study, [name] designed scenarios to test the pharmacy refill function and improve its usability for Veterans; she will develop analogous scenarios for SMMRT in the proposed study. In the precursor project to the work proposed herein, [name] led usability studies to refine and enhance the SMMRT, leading to **two publications recently accepted for publication**:

(4) WORK PROPOSED

Timeline

Research Activity	Month																	
	0	1	2	3	4	5	6	7	8	9	10	11	12	13	14	15	16	17
IRB Approval		x																
AIM 1 (SMMRT RCT)																		
Training of Research Assistant	x																	
Re-introduction of study to clinical stakeholders		x																
Testing data flow processes (med list into SMMRT tool)	x	x																
Recruitment and enrollment (West Roxbury and Brockton)		x	x	x	x	x	x	x	x	x	x	x	x					
SMMRT Intervention Activities	x	x	x	x	x	x	x	x	x	x	x	x	x	x				
Data Collection (30-day follow-up interviews)		x	x	x	x	x	x	x	x	x	x	x	x	x	x			
Data Analyses														x	x	x	x	
Manuscript: Main outcomes of the SMMRT RCT																x	x	x
AIM 2 (Implementation-oriented formative evaluation)																		
Recruitment and enrollment							x	x	x	x								
Telephone interviews								x	x	x								
Transcription and data analysis								x	x	x	x							
Manuscript: Veterans' and Staff experiences with SMMRT											x	x	x	x	x	x	x	x

(4) WORK PROPOSED (continued)

Methods for Aim 1 (SMMRT RCT):

1. Study setting and population

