- Thank you for allowing me the chance to tell you about our study. I would like to ask you a few questions first to see if you meet the requirements for eligibility. Would that be okay?

[figure not shown]
1. **Do you have access to a computer? Y/N** (*If yes, continue. If no skip to question 4*)
2. **Do you use a computer to connect to the internet, say to search websites or for email?**
3. ***If yes, Do you use secure messaging? If no, would you be willing to use it if required for this study?***
4. **Does anyone help you manage your medicines? Y/ N** (*If yes, continue. If no, not eligible, go to Verbal consent*)
5. **Does that person use a computer/ internet/ email? Y/N** (*If yes, continue. If no, not eligible, *Would you be willing to have your caregiver use secure messaging on your behalf if required for this study?**

If no to either 2 or 3: Unfortunately, you do not meet the criteria to participate in this study. Thank you for your time and interest.

→If Yes to 3 and 4, administer the Callahan screener. If patient passes the screener, then the patient is eligible. Continue on to ICF and HIPAA forms.

3. Randomization and intervention

Veterans successfully recruited and consented to participate will be randomly allocated to either UC or UC+SMMRT. Veterans randomized to UC+SMMRT will receive introduction to My HealtheVet and SMMRT. Within 3 business days of discharge, the SMMRT Research Pharmacist will engage with Veterans and/or their designated family members to conduct medication review and reconciliation via Secure Messaging. See randomization scheme below.

After baseline assessment is complete, participants will be randomly assigned via computer program to receive 1) usual care or 2) UC plus pharmacist-mediated medication reconciliation (SMMRT). After opening, the research assistant will inform the Veteran of the “treatment assignment.”

Overview of the Intervention

[figure not shown]
The intervention principally entails the creation of a personalized medication list for each Veteran/subject, incorporating most current data from Vista (the medical record) into a user-friendly PDF-file interface, i.e. the SMMRT. The research pharmacist will send the SMMRT via attachment to Secure Message to the Veteran and will then interact with the Veteran to ensure that the medical record accurately reflects what medications the Veteran is taking.

What Happens in the Intervention?

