The SMMRT Intervention. Figure 4 shows the elements of the SMMRT intervention. In the figure, diamonds show Veteran activity; ovals show pharmacist activity; and dotted boxes show information exchanges.

Not shown in the figure, Veterans will be trained to use MHV while still hospitalized. Starting at top left of the figure, within 3 business days after the Veteran is discharged

FIGURE 4. Flow Diagram of the SMMRT Intervention

home, the pharmacist reviews CPRS, reconciles medications, and prepares the SMMRT, including photographic images (JPEG files) of each medication from the Medication Image Library (MIL). The MIL is a database developed and maintained by VA Consolidated Mail Order Pharmacy *with* pharmacist-validated images for use in medication identification. The MIL has accurate image matches to 99.9% of VA-dispensed medications based on national drug index (NDI) numbers (personal communication, [name], CDW). *Following*

	in CPRS		
Pharmacist reviews CPRS, reconciles medications, prepares SMMRT, including pill images from Medication Image Library (MIL) database	Veteran uploads corrected SMMRT and sends via Secure Message to Pharmacist	Pharmacist clarifies discrepancies via Secure Message or telephone with Veteran	Pharmacist documents medication reconciliation in CPRS, adds PCP co-signer
Pharmacist sends SMMRT to Veteran via Secure Message	Veteran receives, downloads and reviews SMMRT for accuracy		Pharmacist sends final revised SMMRT to Veteran via Secure Message. Loop closed.

Abbreviations:
CPRS=Computerized Patient Record System; SMMRT=Secure Messaging for Medication Reconciliation Tool; PCP=Primary Care Provider

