Preliminary Analyses. In preliminary analyses, descriptive statistics and bivariate associations will be computed. Then we will assess whether there are differences between the study arms for socio-demographic variables. We will assess imbalance formally using Analysis of Variance for continuous variables and Chi Square tests for dichotomous variables. In order to confound any observed effect of the treatment, a covariate must be imbalanced between the arms and also associated with the outcome. Thus, we will judge how plausible confounding is based on the formal tests, the degree of imbalance, and the plausibility of association with the outcome. Primary analysis will not include any potential confounders, but sensitivity analyses will adjust for plausible confounding variables with large imbalance between the arms.

Statistical Analyses. The primary hypothesis is that SMMRT will result in a reduction in 30-day medication discrepancies as compared with UC. The main outcome will be tested by a two-step analysis. First, we will conduct a logistic regression to compare SMMRT vs. UC. We will take an intent-to-treat approach to the analysis; Veterans will be included in our primary analyses regardless of their level of adherence with their assigned intervention. For participants who do not complete the telephone assessment, we will rely on CPRS/CDW data for outcome assessment.

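### The main-outcome paragraph fills missed 30-day interviews from the chart, but the discrepancy count needs the Veteran's own medication list and no chart-only counting rule is given

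*Combined protocol and SAP*

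**What the plan says.** Section (2) defines a discrepancy as "unintentional differences found in the patient's medical record compared with the patient's medication information". Under Methods for Aim 1, Ascertainment of Outcome puts this into practice. The research associate telephones at 30 days, establishes what the Veteran now takes, compares that with the record's list, and grades each discrepancy high, moderate or low by its potential for harm. Sample size and power makes the main outcome the number of medium- plus high-significance discrepancies per patient.

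The Statistical Analyses paragraph describes a logistic regression of the main outcome and an intent-to-treat approach, and says that Veterans enter the primary analyses whatever their adherence. The next sentence is: "For participants who do not complete the telephone assessment, we will rely on CPRS/CDW data for outcome assessment". It is not limited to particular outcomes.

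The following paragraph, on non-response bias, defines drop-outs as Veterans who withdraw or cannot be reached within 60 days. It models completion and fits a weighted logistic regression with inverse probability weights.

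In the SMMRT arm the research pharmacist works with the Veteran "to ensure that the medical record accurately reflects what medications the Veteran is taking", and Figure 4 includes the step "Pharmacist documents medication reconciliation in CPRS, adds PCP co-signer". No expected interview completion rate is stated.

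**The concern.** The outcome has two inputs, and a missed interview removes one of them. What remains can be searched for internal inconsistencies, but that is a different measurement from the 30-day comparison. The plan does not say who would make the count, from which records, or how items would be graded without knowing what the Veteran takes. The rule would have to be chosen later, possibly after the data are seen, and the primary result would mix two measures.

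The arms may also differ in what a chart shows, because the study pharmacist reconciles and documents only in the SMMRT arm. Correcting the record is a legitimate effect of the intervention. The difficulty is that a chart-only count could change by a different amount from the true count, and differently by arm.

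Finally, the plan does not say how the fill and the weighting fit together. Once missing outcomes have been filled, little or nothing is left to weight.

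**Working it through.** **1. How complete is a chart-only count?** In the pilot (section (3)), a pharmacist's chart review found 108 discrepancies in 51 Veterans, or 108/51 = 2.12 each, "mostly medications that the Veteran was taking but were omitted from the" discharge summary or discharge medication list. These were corrected and the tool was sent out; 34 of 51 Veterans returned it. "Of these 34 Veterans, 17 (50%) had additional discrepancies". Section (3) also reports a check of VA's computer-generated list: "60% of ambulatory Veterans had at least one medication discrepancy". So chart review finds something, but not everything.

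**2. Reproducing the stated power.** Inputs from Sample size and power: 120 per arm, two-sided 5%, rates 3.0 versus 2.4 (or 2.0). For Poisson counts, power = Φ(difference / √((sum of the two rates)/n) − 1.96).

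- 3.0 versus 2.4: 0.6/√(5.4/120) = 2.828, power 80.7% (stated 82%).
- 3.0 versus 2.0: 1.0/√(5.0/120) = 4.899, power 99.8% (stated 99.9%).

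These agree with the plan only if all 120 per arm have the interview-based count.

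**3. False results under the fill.** Assumptions: true mean 3.0 in both arms; a share m missing at random within each arm; chart count 2.12 in usual care (the pilot figure, taken soon after discharge and graded differently) and c in the SMMRT arm. The mild gap sets c = 1.70, that is 2.12 × 2.4/3.0. Each arm's mean is 3.0(1 − m) + m × chart count. Its variance is that mean plus m(1 − m)(3.0 − chart count)². The nominal rate in one direction is 2.5%.

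| m | UC mean | SMMRT mean | Difference | SE | z | False wins for SMMRT |
|---|---|---|---|---|---|---|
| 10% | 2.912 | 2.870 | 0.042 | 0.224 | 0.19 | Φ(0.19 − 1.96) = 3.8% |
| 20% | 2.824 | 2.740 | 0.084 | 0.223 | 0.38 | 5.7% |
| 33% | 2.707 | 2.567 | 0.140 | 0.220 | 0.64 | 9.3% |

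Simulation of a count rate ratio gives about 4%, 6% and 9%. Reversing the gap gives the same rates against SMMRT. With equal chart counts and equal missingness the difference is zero and the rate stays at 2.5%. With equal chart counts but 10% missing in one arm and 20% in the other, the difference is 2.912 − 2.824 = 0.088 and the rate is about 6%, in the direction set by which arm loses more.

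**4. A binary outcome.** The plan specifies logistic regression but gives no cut-point. With assumed cut-points of any discrepancy, or three or more, the mild gap gives about 4% to 5% at 20% missing and 7% to 8% at 33%.

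**5. Power with interviewed Veterans only.** The formula in step 2 with n = 108, 96 and 80 gives 76.5%, 71.6% and 63.7%; simulation gives about 77%, 71% and 65%. For comparison, simulated power under the fill is 73%, 63% and 49% if charts show 2.12 in both arms, and 79%, 76% and 75% if charts keep the true ratio.

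**The case against.** The fill can be defended as the conservative intent-to-treat choice: it keeps every randomized Veteran, and the Human Subjects section lists the medical record among the outcome sources. The sentence may have been meant for utilization. Reminders, a letter, rescheduling and a 60-day window may leave few missed interviews. Weighting rests on its own untestable assumption. All of this is fair, and it limits the likely size of the problem. It does not supply the missing rule, and a sentence meant for utilization should say so.

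Some stronger readings are tempting but not supported.

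- A reader might infer that no analysis is named primary. The sentence before the fallback refers to the primary analyses, so the natural reading is that the fill is primary and the weighting is a check on non-response. What is missing is a statement of how the two relate.
- A reader might infer that the two paragraphs concern different non-completers. The definitions largely overlap: a Veteran who withdraws or cannot be reached will ordinarily be one with no telephone assessment.
- A reader might infer that charts show nothing, or that SMMRT charts would be wiped clean, so that false benefit is large. The pilot's 108 discrepancies contradict the first. The second needs the chart to be cleared with no change in the true count, which nothing in the plan suggests. Routine care can also change usual-care records.

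One detail cuts both ways. The pilot's additional discrepancies were most often duplicates across two VA facilities, so what a chart count catches may depend on which records are searched. That is a further item the rule would have to settle.

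**Conclusion.** The concern stands. Followed as written, the primary analysis substitutes an undefined and incomplete measure for Veterans without an interview, and equal chart detection by arm is unsupported. The gap in the rule is certain; the size of any bias is not. There is no false-positive inflation if detection and missingness are equal by arm, although a true effect is diluted if charts show no arm difference. A mild gap gives about 4%, 6% and 9% false results in one direction at 10%, 20% and 33% missing, in favour of either arm, and somewhat less on a binary outcome.

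The missing shares and chart counts are assumptions. The 33% is the pilot's non-return of messages (17 of 51), not a telephone completion rate, and serves only as an upper value. The test is a count rate ratio, not the planned logistic regression.

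**What to change.** In the Statistical Analyses paragraph:

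1. Limit the CPRS/CDW fallback to readmission, emergency department use and community tenure. Note that the plan takes these from chart review plus interview, so chart-only values may miss events known only from the Veteran.
2. Treat the discrepancy outcome as missing when there is no interview list. Handle it with the weighting already planned, using one definition of non-completion and a small prespecified completion model that includes arm.
3. Keep any chart-only count as a sensitivity analysis with a written counting and grading rule, applied unaware of arm where feasible.
4. Add a sensitivity analysis that varies the assumed outcome in non-completers by arm, in both directions, and report interview completion by arm.

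If the sponsor keeps the fill as primary, the minimum is a prespecified chart-only counting and grading rule, and a label of sensitivity on the weighted analysis.

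The cost is mainly wording plus one added analysis. Only interviewed Veterans would then contribute to the primary outcome. Under the count model, power for 3.0 versus 2.4 is about 77%, 71% and 65% at 10%, 20% and 33% missing, so the stated 82% should be described as assuming complete interviews. The argument for the change is validity of the measure, not power, since the fill can have more or less power than this. Weighting corrects only for measured predictors of non-response. At 10% missing there are about 0.10 × 240 = 24 non-completers, which is why the completion model must stay small.
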